It is essential that the transdiagnostic CBT is agreeable to VAMC patients. Thus, structured interviews will be completed with participants at post-treatment and 6-month follow-up to evaluate the presentation, format, and active components of the treatment. The two time points will assess participants immediate (post-treatment) and

delayed (6-month follow-up) reactions to treatment. The interview methodology allows for the acquisition of data through open discussion of predetermined topics as facilitated by the interviewer. Interviews will be conducted by the Project Research Assistant and will follow pre-determined areas of discussion. The discussion will use openended questions, including follow-up probes and examples. These 30-60 minute interviews will be completed with all participants that completed the treatment in the transdiagnostic CBT condition. Interviews will be audio recorded for transcription and interviewers also will keep notes on the discussion.

The following are elicitation questions that will be discussed in the interviews:

- 1. What did you think about the treatment? What do you like about it? What don't you like?
- 2. What aspects of the treatment did you find to be most helpful and why?
- 3. Would you recommend this treatment to other Veterans with similar problems with anxiety/depression? If so (or if not), why?
- 4. Are there any additional things that should be included in the treatment that were not discussed?

At the completion of the interviews, all audio recordings and facilitator notes will be transcribed by the project staff. The overarching goal of the analysis of these data is to identify a set of thematic categories and to assign these categories to higher-order categories to provide a clear picture of the data. Multiple steps will be involved in the analysis of the data:

- 1. *Narrative descriptions.* Specific sections and quotes from the narratives will be carefully selected as exemplars of the content to characterize the general feel of the data.
- 2. Content analysis. This step involves the identification of relevant examples, themes, and patterns in the data. The data will be organized and reviewed by the project team to first develop thematic categories for the relevant quotes and then eventually come to consensus about the themes. The content analysis is based the expectation that important insights will emerge through the evaluation from several different perspectives.
- 3. *Inductive analysis.* The project team will further group the identified themes into categories that are based on information that was obtained from participants (indigenous typologies) and categories observed by the project staff, but not directly articulated by participants (analyst-constructed typologies).
- 4. Logical analysis. Cross-classification process/outcomes matrices will be developed from the categories developed in the previous steps.

Payment to Participant:

Participants will be compensated \$10 for completing the self-report questionnaire packet and \$10 for completing the interviews for each of the 3 assessment periods (pre-treatment, immediate post-treatment, 6-month post-treatment) for a total of \$60. Payment is not contingent on completing the entire questionnaire packet and/or interview; rather, participants still will be compensated \$10 if they begin either the questionnaire packet or the interviews but choose not to complete them fully. A check will be mailed to the address provided by participants after they complete each phase of the assessment (pre-treatment, immediate post-treatment, 6-month post-treatment). This process will likely take appropriately 30-60 days.

Data Entry and Management

All data collected for this study will be specifically collected for research purposes and will not be used for any other purpose. The study database will be maintained in a password-protected system with access limited to authorized members of the research team. Other authorized persons, such as regulatory authorities, also may have access to these records. Regarding security, data will be stored on computers that are password protected, on a secure VAMC server, behind the VAMC firewall, and access is logged. All privacy obligations under the Health Insurance Portability and Accountability Act (HIPAA) will be met. During assembly of the final research database, all participants will be given a study identification. Participant information always will be treated as confidential. The study database will be maintained in a password-protected system with access limited to the Principal Investigator and/or authorized members of the research team.

Our software (logical) security policy has three main components: 1) VAMC standard antiviral protection; 2) password policies; and 3) additional level of firewall protection. The National DVA maintains firewall protection. The backup schedule at the RHJ VAMC consists of fully-verified daily backups. The backup tapes, which are in current rotation, are stored locally.

All data will be entered into an SPSS database. The SPSS database will be created by the Principal Investigator and research assistant will be responsible for all data entry. Data quality and consistency checks (e.g., data range checks) will be integrated as part of the data entry procedure. Data quality will be monitored and assured in several ways: 1) as reported; and 2) as entered into the study database. For the former, all hardcopy data forms will be visually inspected by project staff prior to data entry. Furthermore, a manual comparison of randomly selected data hardcopy forms with data output generated from the SPSS database will be performed, and consistency checks will be generated as part of routine data cleaning procedures. All hardcopies of the data files will be stored in a locked file cabinet behind a locked door in the PI's office at the RHJ VAMC (B530). Hardcopies of the data will be destroyed/shredded at five years after the completion of the study.

Analysis Plan – Treatment Outcome Symptomatology and Feasibility

Preliminary Descriptive Analyses

Univariate descriptive statistics and frequency distributions will be calculated as appropriate for all relevant variables to identify potential departures from distributional assumptions of proposed analyses. If necessary, appropriate data transformations will be applied, or alternative analysis procedures (e.g., nonparametric) will be used. Baseline values for demographic and symptom variables will be described via frequency distributions for categorical variables, measures of central tendency (mean, median), and variability for the total sample and within race groups. The baseline variables will be compared between intervention groups using t-tests (or Wilcoxon rank sum tests) for continuous outcomes and chi-square (or Fisher's Exact Test) for categorical variables.

Missing Data

The full intent to treat (ITT) analysis set will comprise all randomized participants. Missing data in the full analysis set will occur if participants drop out prior to the end of the study. Participants will not be discontinued from the study because of non-adherence and all will remain in the study unless consent is withdrawn or if there are concerns regarding participant safety. Missing data for the ITT analysis set will be imputed using multiple imputation methods. The results of analyses using study completers and protocol adherers (completer and perprotocol analyses) will be compared with results using the ITT analysis set to test sensitivity of study conclusions to study drop-outs and protocol non-adherence. In addition, the information on dropout proportion will be used as one of the outcome measures of intervention feasibility.

Efficacy (Symptomatology & Quality of Life) Measures Analyses (Primary Aim 1)

The continuous measures of intervention efficacy and quality of life are APPQ, DASS, IIRS, MASA, PCL, STICSA, and V/SF-36. The primary outcome time point is at the end of the active intervention phase (immediate post-treatment) and the secondary time point is at the end of the naturalistic 6-month follow-up period. The difference in mean change from baseline to end-of-active intervention (effect sizes) for transdiagnostic CBT versus BAT control condition will be estimated via 95% CI. For the secondary time-point analyses, transdiagnostic CBT versus BAT control differences in change from immediate end-of-intervention to the 6-month follow-up will also be estimated using 95% CI. By assessing the magnitude of the between-intervention-group differences, as described by the CI, clinicians can judge whether the novel intervention provides sufficient improvement in these outcomes to suggest a clinically significant result that warrants further investigation.

In preliminary hypothesis testing, efficacy outcome variables will be compared using the generalized linear mixed models (GLMM) approach. This approach provides a general framework that accommodates a wide range of data types (continuous, ordinal, dichotomous, categorical, count) and distributional assumptions (e.g. Gaussian, Binomial, Poisson) and accommodates repeated measures, covariate structure among repeated observations, and missing data. In the first set of primary hypothesis testing analyses, immediate post-treatment scores for each outcome of interest will be used (separately) as the dependent variable in the model, intervention (transdiagnostic CBT versus BAT control) will be included as the primary independent variable, and pre-treatment scores for the outcome of interest will be added as covariates. When approximate normality is assumed, GLMM reduces to a general linear models (GLM) approach which, in the simplest case (intervention as the primary independent variable with baseline level of outcome variable as covariate), is equivalent to a comparison of change from baseline scores for transdiagnostic CBT versus BAT control using an independent sample t-test. Additional covariates (e.g. age, number of psychiatric comorbidities, race, sex, combat theatre, and number of treatment sessions) will be added to the model to adjust for putative confounding variables. If intervention differences in other baseline variables are found in initial descriptive analyses, these variables will be also be added to the multivariable model. In secondary analyses, the modeling procedure will be repeated for the period between immediate post-treatment and 6-month follow-up. Given that we are seeking preliminary evidence of treatment

efficacy (to justify the next step in this line of research), there will be no adjustment for multiple outcomes or time points to avoid an overly conservative approach at this preliminary stage.

Feasibility and Acceptability Analyses (Primary Aim 2)

Measures of feasibility and acceptability are dropout proportions (dropout y/n), proportion of sessions attended, proportion of homework assignments completed, and patient satisfaction scores on the STTS-R. 95% CI for proportions will be used to estimate the proportion of participants who exit the study prematurely (drop out) within each intervention group and the difference in dropout proportions between the intervention groups. For the treatment satisfaction and adherence outcomes (STTS-R, proportion of missed sessions or homework assignments), the median and mean responses will be obtained within and between each intervention group. 95% CI for difference in means will be used to estimate the between intervention differences in treatment satisfaction (mean STTS-R) and adherence (e.g. average proportion of missed sessions or homework assignments) for the transdiagnostic CBT versus BAT control conditions. Frequency distributions describing the participants' reasons for noncompliance and discontinuation of participation will be developed.

The GLMM modeling framework described for Primary Aim 1 will be used to compare the effect of transdiagnostic CBT versus BAT control on treatment satisfaction, retention (dropout), and treatment adherence (% missed sessions, % homework completion). Dropout proportions (dichotomous outcome) and % of missed visits and % homework completion will be compared between the intervention groups using GLMM, with logistic/binomial regression analyses as special cases for dichotomous and percentage outcomes; STTS-R will be modeled as a continuous outcome using an appropriate link function. We also will model the longitudinal profile of adherence as a dichotomous outcome at each visit (e.g. attended/did not attend a given session). This will allow us to evaluate the trends in session attendance and to determine if the trends differ by intervention (e.g. whether the probability of missing visits is less/greater at earlier or later time points).

Exploratory Analyses - Diagnostic Groups

Exploratory analyses using GLMM modeling, as described above, will be carried out to determine if there is a preliminary suggestion that the effect of the intervention on efficacy and acceptability outcomes differ by principal diagnosis. For these analyses, a diagnosis by intervention group interaction term will be included in the model. Trends toward significance for the diagnosis by intervention interaction term would provide suggestive evidence of a possible differential diagnosis effect, suggesting that the change in the outcome variable is different for disorder groups (e.g., depressive disorders versus anxiety disorders) or between specific disorders (e.g., PTSD versus MDD). It is acknowledged that this study may not be powered to fully evaluate the statistical significance of the diagnostic comparisons; however, for this preliminary study, trends toward statistical significance are sought for future hypothesis-driven study in a larger adequately powered trial, rather than confirmation of a hypothesized differential diagnosis effect. Similar exploratory analyses will be completed for race and combat theatre.

E. PROTECTION OF HUMAN SUBJECTS

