A small number of transdiagnostic treatment approaches have been proposed for the depressive/anxiety disorders (Norton, 2009). Although still in development and preliminary evaluation, early outcomes suggest that transdiagnostic approaches can be delivered efficaciously across the depressive/anxiety disorders, with moderate-to-high effect sizes (Farchione et al., 2012; Norton, 2012; Schmidt et al., 2012). Because transdiagnostic CBT approaches have the potential to address numerous barriers to accessibility and delivery of evidence-based care as discussed earlier, these initial findings are very encouraging. However to date, no transdiagnostic CBT protocols have been developed for or studied in Veterans.

The proposed investigation seeks to study a transdiagnostic CBT protocol for Veterans with depressive/anxiety disorders. The current status of psychosocial treatment for the eight depressive/anxiety disorders targeted in this study necessitates that providers receive specific comprehensive training in eight or more distinct CBTs focused on specific disorders, rather than the more common comorbid presentations of the disorders. The transdiagnostic CBT proposed for evaluation in this study has the potential to reduce the training burden tremendously, and also has the potential to achieve superior outcomes with regard to comorbid depressive/anxiety disorders because the intervention is designed specifically to address the disorders with and without comorbidity. This integrated treatment incorporates evidence-based practices for each of the included disorders, tailoring treatment to Veterans through the completion of OEF/OIF Veteran focus groups and initial piloting in VAMC patients with depressive/anxiety disorders. The treatment aims to improve recovery of VAMC patients with depressive/anxiety disorders by reducing mental health symptoms and improving quality of life. If efficacious, this treatment will have the potential to reduce VAMC provider-training burden and associated costs and improve the quality of care provided to VAMC patients with depressive/anxiety disorders by improving access to CBT.

C. PRELIMINARY STUDIES

Initial Demonstration of Transdiagnostic Protocol

Fifteen VAMC patients were recruited over a 6-month period through the CBT Clinic at the Ralph H. Johnson (RHJ) VAMC to complete the treatment within standard clinical psychotherapeutic practices at the VAMC. All

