participants referred to this clinic already have expressed interest in receiving psychotherapy; and, thus, none of the 15 invited participants refused to participate in treatment. All participants were diagnosed with multiple comorbid depressive/anxiety disorders and reported severe, pre-treatment symptoms of anxiety and depression. PTSD was the most common presenting problem (46.6% PTSD, 26.7% SOC, 26.7% PD, 7.1%) and MDD was the most common comorbid disorder (64.2% MDD, 14.3% SOC, 7.1% PTSD, 7.1% PD). In general, participants were stabilized on multiple psychotropic medications prior to beginning CBT. Twelve of the fifteen participants finished treatment (80.0%). Treatment completers attended an average of 11.5, 50-minute sessions. As presented in the table below, participants demonstrated significant improvements in symptoms of impairment/quality of life, depression, stress, anxiety, and PTSD across all disorders and comorbidities. These findings provide preliminary support for the feasibility of a structured, transdiagnostic CBT protocol for the depressive/anxiety disorders among VAMC patients.

Scale (n)	Pre	Post	t (p)	Effect Size
IIRS-Impairment (12)	66.0 (14.9)	41.2 (19.8)	6.4 (< .001)	1.42
PTSD Checklist (7)	56.1 (13.1)	37.0 (14.0)	5.6 (< .01)	1.41
DASS-Depression (12)	26.2 (10.8)	10.3 (10.3)	5.3 (< .001)	1.51
DASS-Anxiety (12)	25.2 (10.7)	11.8 (9.1)	5.5 (< .001)	1.35
DASS-Stress (12)	26.3 (10.8)	15.7 (9.6)	3.6 (< .01)	1.04

Efficacy of Initial Transdiagnostic CBT in VAMC Patients

Note. Sum scores reported as means (standard deviations). Cohen's ds used for effect sizes.

Focus Group with OEF/OIF Veterans

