The results from the initial demonstration and OEF/OIEF Veteran focus groups were used to inform the revisions of the transdiagnostic CBT protocol. Once the revised protocol was complete, a demonstration of the revised transdiagnostic CBT protocol was initiated, once again, within standard clinical psychotherapeutic practices at the VAMC. The methods of the second demonstration were largely identical to the first demonstration. Thirty-one VAMC patients were recruited to complete the treatment. All participants were diagnosed with multiple comorbid depressive/anxiety disorders and reported severe pre-treatment symptoms. Among the twenty-three treatment completers, PTSD was the most common principal diagnoses (39.1% PTSD, 26.1% MDD, 21.7% PD, 8.7% SOC, and 4.3% OCD) and MDD was the most common comorbidity (43.5% MDD, 26.1% PTSD, 8.7% drug/alcohol abuse, 4.3% PD, 4.3% SOC). Treatment completers attended an average of 11.8, 45-60 minute sessions. As presented in the table below, participants demonstrated significant improvements in symptoms of impairment/quality of life, depression, stress, anxiety, and PTSD across all disorders and comorbidities. These findings provide additional support for the feasibility and likely efficacy of the transdiagnostic CBT protocol for the depressive/anxiety disorders among VAMC patients.

Efficacy of Revised Transdiagnostic CBT in VAMC Patients

Scale (n)	Pre	Post	t (p)	Effect Size
IIRS-Impairment (23)	64.3 (13.1)	37.3 (17.6)	7.3 (<.001)	1.74
PTSD Checklist (22)	56.5 (17.8)	33.7 (14.2)	7.2 (< .001)	1.42
DASS-Depression (23)	12.0 (6.1)	4.8 (4.3)	6.7 (< .001)	1.36
DASS-Anxiety (23)	10.9 (5.4)	5.0 (3.5)	6.2 (< .001)	1.30
DASS-Stress (23)	13.8 (5.1)	7.0 (3.9)	6.1 (< .001)	1.50

Note. Sum scores reported as means (standard deviations). Cohen's ds used for effect sizes.

D. RESEARCH DESIGN AND METHODS

Project Timeline

Project Component	Year	Timeframe
Preparing for RCT	Y01	month 01 – 06
Hiring staff	Y01	month 01 – 03
Training on procedures/protocols	Y01	month 03 – 06
Advertising upcoming trial for recruitment	Y01	month 03 – 06
Randomized controlled trial	Y01-Y04	month 06 – 54
Recruitment and active treatment		month 06 – 45
Ongoing data entry and integrity/fidelity review	VS	month 09 – 42
Data analyses of post-treatment (follow-up)		month 24 – 54
Grant application(s) (e.g., DVA CSR&D Merit)	Y04-Y05	month 36 – 60
Dissemination of findings	Y05	month 54 – 60
Revision of manual based on findings/feedback	Y05	month 54 – 60

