RCT of Transdiagnostic CBT

Objective

To evaluate the transdiagnostic CBT in a RCT of VAMC patients with depressive/anxiety disorders by investigating its preliminary efficacy in reducing symptomatology, comorbidity, and improving quality of life compared to BAT (psychotherapy control condition) at immediate post-treatment and 6-month follow-up. Patient satisfaction and predictors of feasibility (attendance and dropout) also will be assessed.

Recruitment Strategy

VAMC patients will be recruited through the Primary Care – Mental Health Integration program and CBT Clinic at the RHJ VAMC. Within these programs, all VAMC patients reporting symptoms of depression and anxiety meet with a mental health staff member to complete a diagnostic interview and self-report measures as part of their standard clinical practices. If VAMC patients endorse symptoms consistent with a depressive/anxiety disorder, the patient's interest in participating in research will be assessed and, if agreeable to research, patients will be put in contact with research staff (same day meeting and/or follow-up phone to schedule research assessment). A research assessment will be completed with the project staff to first complete consent documentation and then assess inclusion/exclusion criteria (with a targeted sample of 96 VAMC patients; \geq 72 completers), including a semi-structured clinical interview and self-report questionnaires focused on the psychiatric symptoms and quality of life (described later). Participants who meet diagnostic criteria for the targeted disorders will be randomized into a study condition, and will be assigned to a project therapist. Because most VAMC patients who meet study criteria likely will present with multiple depressive/anxiety disorders, principal diagnosis, or the most impairing of

the diagnosable disorders, will be used to select patients for participation. To balance diagnoses across the two conditions, a stratified random assignment based on principal diagnosis will be used for the most common principal diagnoses (MDD, PTSD, and PD). Based on new patient consults at the RJH VAMC (i.e., nearly 1000 in 2011 with at least one-half presenting with symptoms of an depressive/anxiety disorder), it is expected that \geq 50% of the recruited VAMC patients will have served in OEF/OIF and \geq 33% will be representative of minority groups.

Eligibility Criteria

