Inclusion criteria involve: 1) participants must be clearly competent to provide informed consent for research participation; 2) participants must meet DSM diagnostic criteria for a principal diagnosis of a depressive/anxiety disorder (PD, PTSD, SOC, OCD, GAD, specific phobia, MDD, or DD); and 3) participants must be 18 - 80 years old. Exclusion criteria involve: 1) recent history (< 2 months) of psychiatric hospitalization or a suicide attempt as documented in their medical record, 2) current diagnosis of substance dependence or abuse on the structured clinical interview, 3) acute, severe illness or medical condition that likely will require hospitalization and/or otherwise interfere with study procedures as documented in their medical record (e.g., active chemotherapy/radiation treatment for cancer, kidney dialysis, oxygen therapy for chronic obstructive pulmonary disease), 4) recent start of new psychiatric medication (< 4 weeks), 5) diagnosis of traumatic brain injury (TBI) in their medical record and/or endorsement of screener questionnaire regarding the symptoms of TBI modified from the Post-Deployment Health Assessment employed by the Department of Defense, or 6) diagnosis of schizophrenia, psychotic symptoms, personality disorder, and/or bipolar disorder. VAMC patients excluded due to these factors will be reconsidered for participation once the condition related to their exclusion is resolved or stabilized. Together, these inclusion/exclusion criteria should allow the vast majority of interested VAMC patients with depressive/anxiety disorders to be eligible to participate. Ineligible VAMC patients will be referred for nonstudy-related treatments within mental health at the RHJ VAMC.

Procedures

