~33	6-Month Follow-Up Assessment	Clinical interview, immediate treatment interview, & self-report battery (7 measures), treatment satisfaction

Note. Behavior therapy involves the introduction, teaching, in-session and between-session practice, and mastery of behavioral therapeutic techniques designed to improve symptoms of depression and anxiety, including behavioral activation (BAT group) as well as situational, physical, thought, and emotional exposures (transdiagnostic CBT group). Final treatment session will take place between sessions 12-16, as determined by provider and participants' collective decision. Final treatment session will involve relapse prevention content. Post-treatment assessment will be completed 1 week immediately after final treatment session. 6-month follow-up assessment will be completed 6-months after final treatment session.

Randomization Procedures

Participants will be randomly assigned (1:1) to one of the two study arms (*n* = 48 per arm) using a permuted block randomization procedure. Randomization will be stratified by principal diagnostic group and block size will be varied to minimize the likelihood of unmasking. After determining eligibility and completing consent and baseline assessment materials, enrolled participants will be assigned to treatment groups by the Project Research Assistant using a computer generated randomization scheme. Once a participant is randomized and attends the first session, they will be included in the intent-to-treat analysis. Randomization will occur at the participant level. As such, we will take the following steps to minimize contamination between the two arms of the study: 1) only one member of a household will be eligible for enrollment; and 2) other VAMC providers will be informed of their patients' participation in the study, but will be blinded to the treatment condition of their patients.

Transdiagnostic CBT Treatment Condition

As noted above in the Preliminary Studies section, a transdiagnostic CBT protocol was developed and revised through two demonstration studies and one focus group. The resulting protocol involves several primary components, including psychoeducation on the symptoms of depression and anxiety (session 1), assessment of motivation and setup of treatment plans (session 2), exposure therapy (sessions 3-15), and relapse prevention (final session). In addition to these primary components, optional modules are included to supplement exposure

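### Randomisation is stratified by principal diagnosis, but the stratification factor is not named in the primary efficacy model or in the 95% CI for the treatment difference

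*Combined protocol and SAP*

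**What the plan says.** **Eligibility Criteria (section D).** Eight disorders qualify: "principal diagnosis of a depressive/anxiety disorder (PD, PTSD, SOC, OCD, GAD, specific phobia, MDD, or DD").

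**Recruitment Strategy (section D).** To balance diagnoses between arms, "a stratified random assignment based on principal diagnosis will be used for the most common principal diagnoses (MDD, PTSD, and PD"). The handling of the other five is not described.

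**Randomization Procedures (section D).** Allocation is 1:1 in permuted blocks: "Randomization will be stratified by principal diagnostic group and block size will be varied to minimize the likelihood of unmasking". The groups are not listed.

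**Efficacy Measures Analyses, Primary Aim 1.** The difference in mean change is to be given with a 95% CI, with no covariates stated for it. The hypothesis-testing model has arm as the main independent variable and the baseline score as covariate, and then: "Additional covariates (e.g. age, number of psychiatric comorbidities, race, sex, combat theatre, and number of treatment sessions) will be added to the model". Other baseline variables are added if the arms are found to differ on them.

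**Exploratory Analyses - Diagnostic Groups.** Principal diagnosis enters here, through an interaction with arm.

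**The concern.** Stratifying on a factor removes its chance imbalance, so the treatment difference varies less from trial to trial than it would under unrestricted randomisation. An analysis that ignores the factor does not see this gain. It leaves the between-diagnosis variation in the residual and reports a standard error suited to a less efficient design.

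The rule for adding covariates does not repair this. It is triggered by differences between the arms, and stratification is there to prevent such differences on diagnosis. The factor the design controls is therefore among those the rule is least likely to select.

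What is at stake is precision. The protocol asks clinicians to judge from the 95% CI whether the new therapy merits further study. If diagnosis matters to outcome, that interval will be wider than the design warrants, and the trial has only 96 patients.

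**Working it through.** **Inputs from the documents.** N = 96, 1:1, 48 per arm; 95% CI, taken to imply a two-sided 5% test because no alpha is stated; pilot diagnosis shares from section C. The protocol gives no effect size, SD or power, so it has no power figure to reproduce.

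**Assumptions.** Outcome SD 1; true difference 0.5 SD for power; principal diagnosis explains R² = 0, 5, 10 or 20% of outcome variance. Because the primary model already adjusts for the baseline score, R² should be read as the share of variance left after that adjustment. All 96 are analysed.

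**Step 1: pilot counts, used for the stratum sizes.**
- Initial demonstration (15 recruited): "46.6% PTSD, 26.7% SOC, 26.7% PD, 7.1"%. 15 × 0.466 = 7 PTSD; 15 × 0.267 = 4 SOC; 15 × 0.267 = 4 PD. These already make 15; the unlabelled last entry takes the list to 107.1%.
- Revised demonstration (23 completers): "39.1% PTSD, 26.1% MDD, 21.7% PD, 8.7% SOC, and 4.3% OCD". Times 23: 9, 6, 5, 2 and 1.
- Pooled, n = 38: PTSD 16, PD 9, MDD 6, all others 7.
- Share outside the three named diagnoses: 7/38 = 18.4%, and 0.184 × 96 ≈ 18 patients. From either pilot alone: 3/23 × 96 = 12.5, about 13; 4/15 × 96 = 25.6, about 26.

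**Step 2: closed form.** With strata balanced:
- SE reported when the stratum is omitted: √(4/96) = 0.204.
- True SE of the difference: √(4(1 − R²)/96).
- Ratio, reported to true: 1/√(1 − R²).
- Type I error when omitted: 2[1 − Φ(1.96/√(1 − R²))].
- Power when omitted: Φ[(0.5/0.204 − 1.96)/√(1 − R²)].
- Power when included: Φ[0.5/(0.204√(1 − R²)) − 1.96].

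| R² | SE ratio | Type I error, omitted | Power, omitted | Power, included |
|---|---|---|---|---|
| 0 | 1.000 | 0.050 | 0.688 | 0.688 |
| 5% | 1.026 | 0.044 | 0.692 | 0.710 |
| 10% | 1.054 | 0.039 | 0.697 | 0.733 |
| 20% | 1.118 | 0.028 | 0.708 | 0.782 |

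**Step 3: simulation.** 6,000 trials per setting, N = 96, four strata in the proportions 16, 9, 6 and 7 of 38, permuted blocks of 4 and 6 within stratum, least squares with and without stratum terms. The block sizes are assumed.

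| R² | Type I, omitted | Type I, included | Power, omitted | Power, included | Change in power from including (points) |
|---|---|---|---|---|---|
| 0 | 0.050 | 0.048 | 0.666 | 0.662 | −0.3 |
| 5% | 0.044 | 0.049 | 0.686 | 0.707 | 2.0 |
| 10% | 0.038 | 0.048 | 0.689 | 0.727 | 3.8 |
| 20% | 0.028 | 0.046 | 0.707 | 0.782 | 7.5 |

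Monte Carlo error is about √(0.05 × 0.95/6000) = 0.003 for type I error and √(0.7 × 0.3/6000) = 0.006 for each power figure. The two routes agree: with the stratum omitted, the test becomes more conservative as R² grows; with it included, the test stays near its nominal level.

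**The case against.** **The list is open, and diagnosis is modelled elsewhere.** The covariate list begins with e.g., so the sponsor may add diagnosis, and the exploratory models do use it. Hence the factor is unspecified in the primary model, not excluded from it. But an open list does not commit the analysis in advance, and the exploratory models ask whether the effect differs by diagnosis, which is a different question from the main estimate.

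**The size is assumed.** This stands. No document gives an R², and at zero nothing is lost. The baseline score of the same outcome may already carry much of what diagnosis would add.

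**A conservative test is harmless in a preliminary trial.** In part. There is no bias and no excess of false positives. But a trial seeking preliminary evidence of efficacy has reason to keep the power its design has already secured.

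**Two stronger readings that the documents do not support.**
- A reader might infer that patients with the other five diagnoses have no stratum and could split badly between the arms by chance. Randomization Procedures puts all participants in permuted blocks stratified by diagnostic group, and a natural joint reading is that the remainder forms one further group. With a single list in blocks of 4 or 6 (assumed), 18 patients could split no worse than 10:8. The text fails to list the strata; it does not show that the remainder is assigned by simple chance.
- A reader might infer from the pilots that social phobia was as common as MDD and was wrongly passed over. The counts tie (6 and 6 of 38) only when 15 recruited patients are pooled with 23 completers, and one of the two lists has an unlabelled entry. The revised demonstration alone has MDD 6 and social phobia 2, and its top three are the three diagnoses the protocol names. Stratifying on the common diagnoses is not in itself an error.

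**Conclusion.** The point holds in a limited form. The trial randomises within diagnosis groups but does not commit its primary model, or the 95% CI for the difference in mean change, to using those groups. The consequence is a standard error that is too large if diagnosis predicts outcome: by about 3, 5 or 12% at R² of 5, 10 or 20%, with type I error near 0.044, 0.038 or 0.028 and about 2, 4 or 8 points of power lost at a 0.5 SD effect. At R² of zero there is no loss. These sizes rest on the assumed R², the assumed effect, four balanced strata and complete data on 96 patients. The treatment estimate is not biased and no sample size figure changes.

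Separately, Recruitment Strategy and Randomization Procedures do not describe the strata in the same terms, and the group whose handling is unstated is not negligible: about 18 of 96, range 13 to 26. This is a matter of clarification.

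**What to change.** **Main change, in Efficacy Measures Analyses (Primary Aim 1).** State that the randomisation stratum, as used at allocation, is a fixed covariate in every Aim 1 model at both time points, whether or not the arms differ on it. Take the 95% CI for the treatment difference from that model, so that the interval and the test rest on the same analysis.

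**Secondary clarification, in Recruitment Strategy and Randomization Procedures.** List the same strata in both places: PTSD, MDD, PD, and all other eligible principal diagnoses. If the computer-generated scheme already uses different groups, list those and use them in the model.

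**Cost.** Four strata take three degrees of freedom (4 − 1). If the scheme has no list for the remaining diagnoses, one has to be added. No extra patients, visits or assessments are needed.
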